Created on: ddmmmyy hh:mm

Page 1 of N

L16.2.6.1 Listing of Cortisol Response Test Results

Cohort 1

| Patient Number | Visit | Was a Cortisol Response Test conducted? | Date | Basal Sample Draw Time | Injection Time | Post-Injection Draw Time | Basal Cortisol Concentration Level (mcg/100ml) | Post Injection Cortisol Concentration Level (mcg/100ml) | Have Abnormal Adrenal Function? | Have HPA Axis ? |
|----------------|-------|---|------------|------------------------|----------------|--------------------------|--|---|---------------------------------|-----------------|
| xx-xxxx | 1 | Yes | yyyy-mm-dd | hh:mm | hh:mm | hh:mm | xxx | xxx | No | |
| | 3 | Yes | yyyy-mm-dd | hh:mm | hh:mm | hh:mm | xxx | xxx | | No |

Table will continue for other cohorts.

Created on: ddmmmyy hh:mm

Page 1 of N

L16.2.6.2 Listing of HPA Axis Suppression Follow-Up

Cohort 1

| Patient Number | Is The Patient Showing Signs Or Symptoms Of HPA Axis Suppression?/ Was a Cortisol Response Test Conducted? | Follow-Up Test | Date/ Basal Sample Draw Time/ Injection Time/ Post-Injection Draw Time | Basal Cortisol Concentration Level (mcg/100ml) | Post Injection Cortisol Concentration Level (mcg/100ml) | Still Show Signs of HPA Axis Suppression? | Was the Patient Referred to an Endocrinologist |
|----------------|---|----------------|---|---|--|---|--|
| xx-xxxx | Yes/ Yes | Test 1 | yyyy-mm-dd / hh:mm / hh:mm/ hh:mm | xxx | xxx | No | No |

Table will continue for other cohorts.

Created on: ddmmmyy hh:mm

Page 1 of N

L16.2.6.3 Listing of Investigator Global Assessment (IGA)

| Cohort | Patient Number | Visit 1 | Visit 2 | Visit 3 / Early Termination |
|---------------|-----------------------|----------------|----------------|------------------------------------|
| Cohort 1 | xx-xxxx | 0 | 0 | 0 |

Cohort 2

Cohort 3

Cohort 4

Created on: ddmmmyy hh:mm

Page 1 of N

L16.2.6.4 Listing of Percent BSA Affected with Atopic Dermatitis

| Cohort | Patient Number | Visit 1 | Visit 2 | Visit 4 / Early Termination | Baseline Total BSA (m²) |
|---------------|-----------------------|----------------|----------------|------------------------------------|---|
| Cohort 1 | xx-xxxx | xxx | xxx | xxx | x.xx |

Cohort 2

Cohort 3

Cohort 4

Created on: ddmmmyy hh:mm

Page 1 of N

L16.2.6.5 Listing of Eczema Area and Severity Index (EASI)

| Cohort | Patient Number | Visit | Location | Erythema | Induration, Papulation, Lichenification | | | Total Grade | Total EASI Score | | |
|----------|----------------|-------|-------------|----------|---|---|---|-------------|------------------|--|--|
| | | | | | Edema | | | | | | |
| Cohort 1 | xx-xxxx | 1 | Head/Neck | 0 | 0 | 0 | 0 | 0 | xxxx | | |
| | | | Upper Limbs | 0 | 0 | 0 | 0 | 0 | 0 | | |
| | | | Trunk | 1 | 1 | 1 | 1 | 1 | 4 | | |
| | | | Lower Limbs | 0 | 0 | 0 | 0 | 0 | 0 | | |
| | | | | 2 | | | | | | | |
| | | | | 3 | | | | | | | |

Cohort 2
Cohort 3
Cohort 4

Created on: ddmmmyy hh:mm

Page 1 of N

L16.2.6.6 Listing of Pruritis Assessment

| Cohort | Patient Number | Visit 1 | Visit 2 | Visit 3/Early Termination |
|---------------|-----------------------|----------------|----------------|----------------------------------|
| Cohort 1 | xx-xxxx | 0 (None) | 1 (Mild) | 1 (Mild) |

Cohort 2

Cohort 3

Cohort 4

Created on: ddmmmyy hh:mm

Page 1 of N

L16.2.6.7 Listing of Application Site Reaction

| Cohort | Patient Number | Visit | Sign / Symptom | | | | | |
|----------|----------------|-------|----------------|---------|-------|------|---------|---------|
| | | | Burning | Erosion | Edema | Pain | Itching | Dryness |
| Cohort 1 | xx-xxxx | 1 | 0 | 0 | 0 | 1 | 0 | 0 |
| | | 2 | 0 | 1 | 0 | 0 | 0 | 0 |
| | | 3 | 0 | 0 | 0 | 1 | 0 | 0 |
| Cohort 2 | | | | | | | | |
| Cohort 3 | | | | | | | | |
| Cohort 4 | | | | | | | | |

Created on: ddmmmyy hh:mm

Page 1 of N

L16.2.7 Listing of Adverse Events by Cohort

| Cohort | Patient Number | Body System / MedDRA Term / AE Term | Treatment Area | Start /End Date | Severity | Relationship to Study Drug | Outcome | Action Taken/ Other Action Taken | SAE? |
|---------------|-----------------------|--|-----------------------|-------------------------|-----------------|-----------------------------------|----------------|---|-------------|
| Cohort 1 | xx-xxxx | Nervous system disorders / Headache / Headache | No | yyyy-mm-dd / yyyy-mm-dd | Mild | Not Related | Recovered | Dose Not Changed/ None | No |

Cohort 2

Cohort 3

Cohort 4

Related = Possible, Probable, Definite

Created on: ddmmmyy hh:mm

Page 1 of N

L16.2.8.1 Listing of Positive Pregnancy Test Results

| Cohort | Patient Number | Visit 1 | Visit 2 | Visit 3 |
|----------|----------------|----------|----------|----------|
| Cohort 1 | xx-xxxx | Negative | Negative | Negative |

Cohort 2
Cohort 3
Cohort 4

Created on: ddmmmyy hh:mm

Page 1 of N

L16.2.8.2 Listing of Abnormal Vital Signs

| Cohort | Patient Number | Age | Visit | Vital Sign | Normal Range | Result |
|---------------|-----------------------|------------|--------------|-------------------|---------------------|---------------|
| Cohort 1 | XX-XXXX | XXX | 1 | Diastolic BP | XXX - XXX | XXX |
| | | | 2 | | | |
| | | | 3 | | | |

Cohort 2
Cohort 3
Cohort 4

Created on: ddmmmyy hh:mm

Page 1 of N

L16.2.8.3 Listing of Abnormal Physical Examination Results

| Cohort | Patient Number | Visit | System | Results |
|----------|----------------|-------|--------|-----------------|
| Cohort 1 | xx-xxxx | 1 | HEENT | Abnormal (Scar) |

2
3

Cohort 2
Cohort 3
Cohort 4

Created on: ddmmmyy hh:mm

Page 1 of N

L16.2.8.4 Listing of Clinical Hematology Laboratory Results

| Cohort | Patient Number | Visit | Hematocrit (unit) | WBC (unit) | Platelets (unit) | Hemoglobin (unit) | etc. |
|----------|----------------|--------|----------------------|---------------|---------------------|----------------------|------------|
| Cohort 1 | xx-xxxx | 1 3 | xxx xxx | xxx xxx | xxx xxx | xxx xxx (Low) | xxx xxx |

Cohort 2

Cohort 3

Cohort 4

Created on: ddmmmyy hh:mm

Page 1 of N

L16.2.8.5 Listing of Clinical Chemistry Laboratory Results

| Cohort | Patient Number | Visit | Alkaline Phosphatase (unit) | Alnine (unit) | Aspartate Transaminase (unit) | Blood Urea Nitrogen (unit) | etc. |
|----------|----------------|--------|--------------------------------|------------------|----------------------------------|-------------------------------|------------|
| Cohort 1 | xx-XXXX | 1 3 | XXX XXX | XXX XXX | XXX (High) XXX | XXX XXX | XXX XXX |

Cohort 2

Cohort 3

Cohort 4

Created on: ddmmmyy hh:mm

Page 1 of N

NOVUM PHARMACEUTICAL RESEARCH SERVICES
STATISTICAL ANALYSIS PLAN

Desoximetasone 0.15% Topical Spray

Protocol / Study No. DSXS 1502a / 71615002

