7.3.1 Adverse Events

All the adverse events (AEs) reported throughout the study will be coded and classified according to the MedDRA (Medical Dictionary for Regulatory Activities) coding dictionary (Version 19 or higher). Each adverse event is to be evaluated for date of start and end, seriousness, severity, causal relationship with the study drugs, action taken and outcome.

A summary table of the number and percent of patients with AEs by system organ class, preferred term, and cohort will be presented. Each patient will be counted only once within each preferred term.

A frequency summary table of the number of AEs by system organ class, preferred term, severity, and cohort will be presented. Severity will be classified as “Mild”, “Moderate”, or “Severe”.

Similarly, a frequency summary table of the number of AEs by system organ class, preferred term, and relationship to a study drug, and cohort will be presented. Relationship to a study drug will be classified as “Not Related” or “Related” where “Related” includes “Possible”, “Probable”, or “Definite”.

Should sufficient data exist, adverse event frequencies will be compared between cohorts using Fisher’s exact test.

All AEs will be listed by cohort and patient.

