| Not Related | xx (xx.x%) | xx (xx.x%) | xx (xx.x%) | xx (xx.x%) | xx (xx.x%) |
| Related | xx (xx.x%) | xx (xx.x%) | xx (xx.x%) | xx (xx.x%) | xx (xx.x%) |
| Death | xx (xx.x%) | xx (xx.x%) | xx (xx.x%) | xx (xx.x%) | xx (xx.x%) |
| Serious AE | xx (xx.x%) | xx (xx.x%) | xx (xx.x%) | xx (xx.x%) | xx (xx.x%) |

Related = Possible, Probable, Definite

Created on: ddmmmyy hh:mm

Page 1 of N

**T16.1.9.10.1 Summary of Frequency of All Adverse Events by Body System
(Safety Population)**

| Body System | MedDRA Term | Cohort | Events | Patients | Fisher's p-value |
|-------------------------------|-------------|-----------------|--------|------------|------------------|
| Patients with at least one AE | Total | Cohort 1 (N=xx) | xx | xx (xx.x%) | x.xxxx |
| | | Cohort 2 (N=xx) | xx | xx (xx.x%) | |
| | | Cohort 3 (N=xx) | xx | xx (xx.x%) | |
| | | Cohort 4 (N=xx) | xx | xx (xx.x%) | |
| Ear and labyrinth disorders | Ear pain | Cohort 1 (N=xx) | xx | xx (xx.x%) | x.xxxx |
| | | Cohort 2 (N=xx) | xx | xx (xx.x%) | |
| | | Cohort 3 (N=xx) | xx | xx (xx.x%) | |
| | | Cohort 4 (N=xx) | xx | xx (xx.x%) | |

N = Total number of patient in each cohort; Percentage is based on total number of patients.

Created on: ddmmmyy hh:mm

Page 1 of N

**T16.1.9.10.2 Summary of Frequency of All Adverse Events in $\geq 2\%$ of Patients by Body System
(Safety Population)**

**T16.1.9.11 Summary of Frequency of All Adverse Events by Severity
(Safety Population)**

| Body System | MedDRA Term | Cohort | Mild | Moderate | Severe |
|-------------------------------|--------------------|-----------------|-------------|-----------------|---------------|
| Patients with at least one AE | Total | Cohort 1 (N=xx) | xx (xx.x%) | xx (xx.x%) | xx (xx.x%) |
| | | Cohort 2 (N=xx) | xx (xx.x%) | xx (xx.x%) | xx (xx.x%) |
| | | Cohort 3 (N=xx) | xx (xx.x%) | xx (xx.x%) | xx (xx.x%) |
| | | Cohort 4 (N=xx) | xx (xx.x%) | xx (xx.x%) | xx (xx.x%) |
| Ear and labyrinth disorders | Ear pain | Cohort 1 (N=xx) | xx (xx.x%) | xx (xx.x%) | xx (xx.x%) |
| | | Cohort 2 (N=xx) | xx (xx.x%) | xx (xx.x%) | xx (xx.x%) |
| | | Cohort 3 (N=xx) | xx (xx.x%) | xx (xx.x%) | xx (xx.x%) |
| | | Cohort 4 (N=xx) | xx (xx.x%) | xx (xx.x%) | xx (xx.x%) |

N = Total number of events in each cohort; Percentage is based on total number of events.

Created on: ddmmmyy hh:mm

Page 1 of N

**T16.1.9.12 Summary of Frequency of All Adverse Events by Relationship
(Safety Population)**

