| Body System | MedDRA Term | Cohort | Related | Not Related |
|-------------------------------|--------------------|-----------------|----------------|--------------------|
| Patients with at least one AE | Total | Cohort 1 (N=xx) | xx (xx.x%) | xx (xx.x%) |
| | | Cohort 2 (N=xx) | xx (xx.x%) | xx (xx.x%) |
| | | Cohort 3 (N=xx) | xx (xx.x%) | xx (xx.x%) |
| | | Cohort 4 (N=xx) | xx (xx.x%) | xx (xx.x%) |
| Ear and labyrinth disorders | Ear pain | Cohort 1 (N=xx) | xx (xx.x%) | xx (xx.x%) |
| | | Cohort 2 (N=xx) | xx (xx.x%) | xx (xx.x%) |
| | | Cohort 3 (N=xx) | xx (xx.x%) | xx (xx.x%) |
| | | Cohort 4 (N=xx) | xx (xx.x%) | xx (xx.x%) |

N = Total number of events in each cohort; Percentage is based on total number of events.

Related = Possible, Probable, Definite

Created on: ddmmmyy hh:mm

Page 1 of N

**T16.1.9.13 Summary of Frequency of Serious Adverse Events
(Safety Population)**

| Body System | MedDRA Term | Cohort 1 N=xx | Cohort 2 N=xx | Cohort 3 N=xx | Cohort 4 N=xx |
|--|------------------------|--------------------------|--------------------------|--------------------------|--------------------------|
| Injury, poisoning and procedural complications | Alcohol poisoning | xx | xx | xx | xx |

Created on: ddmmmyy hh:mm

Page 1 of N

**T16.1.9.14 Summary of Shift Analysis of Clinical Laboratory Assessments (Chemistry) from Baseline to Day 28
(Safety Population)**

Alanine Aminotransferase (U/L)

| | Cohort 1 (N=xx) | | | Cohort 2 (N=xx) | | | Cohort 3 (N=xx) | | | Cohort 4 (N=xx) | | |
|------------|--------------------|---------------|---------------|--------------------|---------------|---------------|--------------------|---------------|---------------|--------------------|---------------|---------------|
| Baseline-> | Low | Normal | High |
| Endpoint | xx (xx.x%) | xx (xx.x%) | xx (xx.x%) |
| Low | xx (xx.x%) | xx (xx.x%) | xx (xx.x%) |
| Normal | xx (xx.x%) | xx (xx.x%) | xx (xx.x%) |
| High | xx (xx.x%) | xx (xx.x%) | xx (xx.x%) |

Table will continue for other lab parameters.

Similar table will be created for T16.1.9.18.

**T16.1.9.15 Summary of Shift Analysis of Clinical Laboratory Assessments (Hematology) from Baseline to Day 28
(Safety Population)**

**T16.1.9.16 Summary of Frequency of Pruritis Assessment
(Safety Population)**

| Visit | Score | Cohort 1 (N = xx) | Cohort 2 (N = xx) | Cohort 3 (N = xx) | Cohort 4 (N = xx) |

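### The AE severity and relationship tables label their total block as patients but count events, and no planned summary defines the share of children with a severe or drug-related AE

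*SAP*

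**What the plan says.** SAP 7.3.1 plans three AE summaries.

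- The first is patient-based: "A summary table of the number and percent of patients with AEs by system organ class, preferred term, and cohort will be presented". Its counting rule follows: "Each patient will be counted only once within each preferred term".
- The second is event-based: "A frequency summary table of the number of AEs by system organ class, preferred term, severity, and cohort will be presented".
- The third, by relationship, is also event-based; it reads, in part, "a frequency summary table of the number of AEs by system organ class, preferred term, and relationship to a study drug, and cohort will be". The SAP then reduces relationship to two classes, with possible, probable and definite pooled as related.

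The shells in SAP section 8 follow this in part.

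- T16.1.9.10.1 (by body system) defines N and its percentages by patients. It has no severity or relationship columns.
- T16.1.9.11 and T16.1.9.12 open with the block "Patients with at least one AE" and carry the footnote "N = Total number of events in each cohort; Percentage is based on total number of events".
- T16.1.9.9 (overall summary) gives patient rows for any AE and for discontinuation due to an AE. Below these comes a row for the number of AEs reported, then severity, relationship, death and serious AE rows with percentages. No footnote says what the percentages are of.
- T16.1.9.13 gives serious AE counts without percentages.
- L16.2.7 lists every AE by cohort and patient, with severity, relationship and a serious flag.

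Protocol section 8.0 and SAP section 2 make the AE profile a secondary objective. The Safety Parameters entry of the protocol synopsis promises summary tables of type, incidence, severity and relationship.

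**The concern.** A block labelled as patients cannot have an event total as its N. The same label opens T16.1.9.10.1, where N is patients, so it changes meaning from one table to the next. The programmer must choose between label and footnote, and a reader may take an event percentage for patient incidence.

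Correcting the label would still leave a gap. How many children had a severe AE, and how many had one judged related to the drug, are basic questions for an AE profile. No planned summary is defined to answer either. With 5 to 10 children in each of Cohorts 2 to 4, one child with repeated events can dominate an event percentage.

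**Working it through.** The plan states no figure to reproduce. The check has two parts.

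**1. Does any planned AE output define the share of children with a severe or related AE?**

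| Output | Unit counted | Split by severity or relationship | Defines the share? |
|---|---|---|---|
| T16.1.9.9, any-AE and discontinuation rows | Patients | No | No |
| T16.1.9.9, severity and relationship rows | Not stated; position suggests events | Yes | No |
| T16.1.9.10.1 and T16.1.9.10.2 | Patients | No | No |
| T16.1.9.11, T16.1.9.12 | Events by footnote, patients by label | Yes | No |
| T16.1.9.13 | Counts only, serious AEs | No | No |
| L16.2.7 | Listing by patient | Recorded per AE | Only by hand count |

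No rule for worst severity per patient, or for any related AE per patient, appears in SAP 7.3.1 or in the shells.

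**2. Can the event percentage stand in for the patient share?**

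Let a cohort have *n* children, *E* events and *S* severe events, with *S* at least 1. The planned table prints *S*/*E*. The number of children with a severe event is at least 1 and at most min(*S*, *n*), so the patient share lies between 1/*n* and min(*S*, *n*)/*n*. Cohort sizes are from SAP section 3: 10 to 20 in Cohort 1, and 5 to 10 in each of Cohorts 2 to 4. The documents give no event counts, so *E* and *S* below are assumptions.

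| *S* of *E* | Table prints | Share of children, *n* = 5 | *n* = 10 | *n* = 20 |
|---|---|---|---|---|
| 1 of 9 | 11.1% | 20% | 10% | 5% |
| 2 of 8 | 25.0% | 20% to 40% | 10% to 20% | 5% to 10% |
| 5 of 10 | 50.0% | 20% to 100% | 10% to 50% | 5% to 25% |
| 5 of 20 | 25.0% | 20% to 100% | 10% to 50% | 5% to 25% |

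First row, *n* = 5: 1/9 = 11.1% is printed and the share of children is 1/5 = 20%, so the table understates it. Third row, *n* = 5: 5/10 = 50% is printed. If all five severe events fall in one child the share is 1/5 = 20%, and the table overstates it. If they fall in five children the share is 5/5 = 100%, and the table understates it. The printed percentage alone cannot be converted to a share of children, and its error has no fixed direction.

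**The case against.** The strongest reply is that the event basis is deliberate. SAP 7.3.1 specifies numbers of AEs for both tables and the footnotes agree with it, so the only error is a row label that is correct in T16.1.9.10.1 and looks carried over. Relabelling it as total AEs would remove the contradiction. The protocol synopsis does not ask for patient incidence within each severity or relationship class. SAP section 8 also says that the shells are a general layout and that headers and footnotes may change.

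Much of this stands: the event basis is intended, and relabelling would cure the contradiction. It would not supply the patient share. Leaving the denominator to be settled after the data are analysed is what a SAP should avoid.

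Four stronger readings are tempting and are not supported.

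- A reader might infer that the patient share can never be obtained. L16.2.7 holds the data by patient, and with 25 to 50 children a hand count is feasible.
- A reader might infer that T16.1.9.9 uses event denominators. Its layout suggests so, but no denominator is stated.
- A reader might infer that event percentages always dilute severe or related AEs. They can also inflate them.
- A reader might infer that the once-per-preferred-term rule contradicts the event tables. It belongs to the patient-based summary.

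The application site reaction table, T16.1.9.17, does summarise severity by cohort for burning, itching, dryness and similar signs. These are scored assessments rather than coded AEs, so it answers the question only in part.

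**Conclusion.** The point holds as a minor reporting defect. The label and footnote of T16.1.9.11 and T16.1.9.12 contradict each other, the percentage rows of T16.1.9.9 below the AE count have no stated base, and no planned summary table defines the number and percent of children with a severe or related AE. The first two follow directly from the SAP text, and the third from a check of each planned AE output.

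The size of any distortion cannot be known in advance, because it depends on how events cluster within children. The worked figures show what is possible under assumed counts; they are not a forecast. The primary HPA axis analysis does not use these tables and is unaffected.

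**What to change.** - **T16.1.9.11 and T16.1.9.12:** count each patient once per term and once overall, at worst severity in the first table and as related if any AE is related in the second. The second rule suits the two relationship classes of SAP 7.3.1. Use dosed patients in the cohort (the safety population) as the denominator. Keep event numbers in a separate column of plain counts, labelled as events, and rewrite the footnotes to match.
- **T16.1.9.9:** state the denominator of every row, and use patients for the severe, related, serious AE and death percentages.
- **SAP 7.3.1:** add the two per-patient counting rules, so that text and shells agree.

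The cost is a text edit, shell changes and programming. The data needed are already recorded by patient for L16.2.7, so nothing new has to be collected.

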### 9.4.6 Compliance

Patients will be provided with a diary with instructions to record the time and date of dosing. Patients will be asked to also record any adverse events and concomitant medications taken during the study.

Patients will dose twice daily for 28 days. All patients who are enrolled and used at least 75%-125% of scheduled doses of the study drug and have data from a post-treatment cortisol response test will be included in the analysis.

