#### 10.1.3 Safety Analysis of Potential HPA Axis Suppression

Dosing will be twice a day for 28 days excluding the doses prior to the Cortisol Response Test (54 applications). All patients who are enrolled, use at least 42 doses of the study drug and have data

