## **CONFIDENTIAL PROTOCOL**

An Open Label, Safety Study to Assess the Potential for Adrenal Suppression Following Treatment with Desoximetasone 0.15% Topical Spray (Taro Pharmaceuticals U.S.A., Inc.) in Patients with Atopic Dermatitis

---

from a post-treatment cortisol response test will be included in the analysis. Patients who have not used 42 doses of the study drug will be excluded from the primary analysis of HPA axis suppression.

The primary analysis of interest is the proportion of patients in each group who are considered to have demonstrated possible HPA axis suppression following treatment with the study medication. As a secondary analysis of the data a logistic regression of the proportion of patients in the study with HPA axis suppression will be performed with %BSA affected as a covariate. See Appendix E for results from the cortisol response test considered indicative of potential HPA axis suppression.

The study will be enrolled by Cohort starting with Cohort 1 and each cohort will be reviewed for the potential of HPA axis suppression. If at least 50% of patients in Cohort 1 experience HPA axis suppression once the minimum number of patients has been enrolled and completed the cohort, enrollment for that cohort will be stopped and no further cohorts will be initiated. If at least 35% of patients have experienced HPA axis suppression across cohorts combined during the study, enrollment will be discontinued and no other cohorts will be initiated. Cohort 2 will not begin until safety data has been reviewed for Cohort 1. The same process will be followed for each Cohort until the study is complete.

For all patients the actual amount of desoximetasone (mg) applied during the study will be calculated from recorded bottle weights and presented.

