7.2 Safety Analysis of Potential HPA Axis Suppression

Dosing will be twice a day for 28 days excluding the doses prior to the Cortisol Response Test (54 applications). All patients who are enrolled, use at least 42 doses of the study drug and have data from a post-treatment cortisol response test will be included in the analysis. Patients who have not used 42 doses of the study drug will be excluded from the primary analysis of HPA axis suppression.

The primary analysis of interest is the proportion of patients in each group who are considered to have demonstrated possible HPA axis suppression following treatment with the study medication. As a secondary analysis of the data a logistic regression of the proportion of patients in the study with HPA axis suppression may be performed with %BSA affected as a covariate. This will depend on the distribution of the %BSA data collected.

The study will be enrolled by Cohort starting with Cohort 1 and each cohort will be reviewed for the potential of HPA axis suppression. If at least 50% of patients in Cohort 1 experience HPA axis suppression once the minimum number of patients has been enrolled and completed the cohort, enrollment for that cohort will be stopped and no further cohorts will be initiated. If at least 35% of patients have experienced HPA axis suppression across cohorts combined during the study, enrollment will be discontinued and no other cohorts will be initiated. Cohort 2 will not begin until safety data has been reviewed for Cohort 1. The same process will be followed for each Cohort until the study is complete.

For all patients the actual amount of desoximetasone (mg) applied during the study will be

NOVUM PHARMACEUTICAL RESEARCH SERVICES
STATISTICAL ANALYSIS PLAN

Desoximetasone 0.15% Topical Spray

Protocol / Study No. DSXS 1502a / 71615002

calculated from recorded bottle weights and presented.

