|-------|----------|----------------------|----------------------|----------------------|----------------------|
| 1 | None | xx (xx.x%) | xx (xx.x%) | xx (xx.x%) | xx (xx.x%) |
| | Mild | xx (xx.x%) | xx (xx.x%) | xx (xx.x%) | xx (xx.x%) |
| | Moderate | xx (xx.x%) | xx (xx.x%) | xx (xx.x%) | xx (xx.x%) |
| | Severe | xx (xx.x%) | xx (xx.x%) | xx (xx.x%) | xx (xx.x%) |
| 2 | None | xx (xx.x%) | xx (xx.x%) | xx (xx.x%) | xx (xx.x%) |
| | Mild | xx (xx.x%) | xx (xx.x%) | xx (xx.x%) | xx (xx.x%) |
| | Moderate | xx (xx.x%) | xx (xx.x%) | xx (xx.x%) | xx (xx.x%) |
| | Severe | xx (xx.x%) | xx (xx.x%) | xx (xx.x%) | xx (xx.x%) |

3

Created on: ddmmmyy hh:mm

Page 1 of N

**T16.1.9.17 Summary of Application Site Reaction
(Safety Population)**

| Sign / Symptom | Visit | Statistic | Cohort 1 (N = xx) | Cohort 2 (N = xx) | Cohort 3 (N = xx) | Cohort 4 (N = xx) | |
|----------------|-------|-----------|----------------------|----------------------|----------------------|----------------------|--|
| Burning | 1 | Absent | xxx (xx.x%) | xxx (xx.x%) | xxx (xx.x%) | xxx (xx.x%) | |
| | | Mild | xxx (xx.x%) | xxx (xx.x%) | xxx (xx.x%) | xxx (xx.x%) | |
| | | Moderate | xxx (xx.x%) | xxx (xx.x%) | xxx (xx.x%) | xxx (xx.x%) | |
| | | Severe | xxx (xx.x%) | xxx (xx.x%) | xxx (xx.x%) | xxx (xx.x%) | |
| 2 | | | | | | | |
| 3 | | | | | | | |
| Erosion | | | | | | | |
| Erosion | | | | | | | |
| Edema | | | | | | | |
| Pain | | | | | | | |
| Itching | | | | | | | |
| Dryness | | | | | | | |

L16.2.1 Listing of Discontinued Patients

| Cohort | Patient Number | Discontinuation Reason |
|---------------|-----------------------|--|
| Cohort 1 | xx-XXXX xx-XXXX | Withdrawal by Subject Lost to Follow-up |

Cohort 2
Cohort 3
Cohort 4

Created on: ddmmmyy hh:mm

Page 1 of N

L16.2.2 Listing of Protocol Deviations

| Cohort | Patient Number | Event Description |
|---------------|-----------------------|--------------------------------|
| Cohort 1 | xx-xxxx | Outside Visit Window (Visit 3) |

Cohort 2
Cohort 3
Cohort 4

Created on: ddmmmyy hh:mm

Page 1 of N

L16.2.3 Patients Excluded from Safety Analysis of Potential HPA Axis Suppression

| Cohort | Patient Number | Exclusion Reason |
|---------------|-----------------------|---|
| Cohort 1 | xx-xxxx | Patient has not used 42 doses of the study drug |

Cohort 2
Cohort 3
Cohort 4

Created on: ddmmmyy hh:mm

Page 1 of N

L16.2.4.1 Listing of Demographic Data

| Cohort | Patient Number | Age | Gender | Ethnicity | Race |

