|---------------|-----------------------|------------|---------------|------------------------|---------------------------|
| Cohort 1 | xx-xxxx | 11 | Female | Not Hispanic or Latino | Black or African American |

Cohort 2

Cohort 3

Cohort 4

Created on: ddmmmyy hh:mm

Page 1 of N

L16.2.4.2 Listing of Medical History

| Cohort | Patient Number | System | Diagnosis or Surgical Procedure | Start Date | End Date | Ongoing |
|---------------|-----------------------|---------------|--|-------------------|-----------------|----------------|
| Cohort 1 | xx-xxxx | Gynecologic | Menopause | yyyy-mm-dd | yyyy-mm-dd | |

Cohort 2

Cohort 3

Cohort 4

Created on: ddmmmyy hh:mm

Page 1 of N

L16.2.4.3 Listing of Concomitant Medication

| Cohort | Patient Number | Treatment Area | Medication | Dosage | Frequency | Route | Start/End Date | Indication |
|---------------|-----------------------|-----------------------|-------------------|---------------|------------------|--------------|----------------------------|-------------------|
| Cohort 1 | xx-xxxx | No | Lisinopril | 20 MG | QD | PO | yyyy-mm-dd / yyyy-mm-dd | Hypertension |

Cohort 2

Cohort 3

Cohort 4

Created on: ddmmmyy hh:mm

Page 1 of N

L16.2.5.1 Listing of Drug Administration

| Cohort | Patient Number | Date of First Dose | Date of Last Dose | Total Doses Applied | Compliance (%) |
|---------------|-----------------------|---------------------------|--------------------------|----------------------------|-----------------------|
| Cohort 1 | xxxx | yyyy-mm-dd | yyyy-mm-dd | xx | xx.x |

Cohort 2
Cohort 3
Cohort 4

Note to programmer:

Compliance = [Total number of applications] / [Planned number of applications] * 100%, where Planned number of applications is determined as follows:

for subjects who completed the study successfully: 56 applications (28 days of twice daily dosing);

for subjects who discontinued early: the minimum between 56 and [(Date of Discontinuation – Date of First Application)].

Created on: ddmmmyy hh:mm

Page 1 of N

L16.2.5.2 Listing of Study Medication Weight

| Cohort | Patient Number | Bottle 1 | | Bottle 2 | | Total Amount Applied (g) |
|----------|----------------|----------------|----------------------|----------------|----------------------|--------------------------|
| | | Date Dispensed | Weight Dispensed (g) | Date Collected | Weight Collected (g) | |
| Cohort 1 | xxxx | yyyy-mm-dd | xx | yyyy-mm-dd | xx | xxx |

Cohort 2

Cohort 3

Cohort 4

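### SAP L16.2.5.1 divides twice-daily applications by a count of days for early discontinuers, which doubles their listed Compliance (%); the primary HPA set is unaffected

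*SAP*

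**What the plan says.** The formula is in SAP section 8, in the programmer note under L16.2.5.1 (Listing of Drug Administration). Compliance is total applications divided by planned applications, times 100%. The planned number has two branches:

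- Completers: "for subjects who completed the study successfully: 56 applications (28 days of twice daily dosing".
- Early discontinuers: "for subjects who discontinued early: the minimum between 56 and [(Date of Discontinuation – Date of First Application".

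The planned count is stated differently where the HPA analysis is described. Protocol 10.1.3 says "Dosing will be twice a day for 28 days excluding the doses prior to the Cortisol Response Test (54 applications", and SAP 7.2 repeats it.

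The rule for entering the HPA analysis also appears in two forms. Protocol 9.4.6 states "Patients will dose twice daily for 28 days" and then admits patients who "used at least 75%-125% of scheduled doses of the study drug" and have a post-treatment cortisol test. Protocol 10.1.3 and SAP 7.2 instead require that patients "use at least 42 doses of the study drug" and have that test, with no upper limit. Protocol 10.1.3 adds: "Patients who have not used 42 doses of the study drug will be excluded from the primary analysis of HPA axis suppression". The specimen reason in the exclusion listing L16.2.3 follows the same rule: "Patient has not used 42 doses of the study drug".

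**The concern.** A ratio of applications to planned applications needs both terms in applications. The completer branch meets this, since 56 is explained as 28 days at two a day. The early-discontinuer branch does not, because subtracting one date from another gives days. No other section of either document supplies the missing factor of 2.

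Protocol 9.6.11 and 9.6.12 call a patient non-compliant below 75% or above 125% of the doses. Read against those limits, the printed column would make an adherent patient who stopped early look like a heavy over-user, and a patient who took half the doses look fully compliant. In a study of systemic steroid effect, that misleads anyone reading exposure off the listing.

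Two smaller points come with it. The planned count is 56 in the listing and 54 in the analysis sections, and the HPA inclusion rule is worded in two ways. SAP 7.7, which lists departures from the protocol's planned analyses, mentions neither.

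**Working it through.** **Inputs.** Two applications a day for 28 days (protocol 9.4.1 and 9.4.6). The formula and both branches come from SAP L16.2.5.1. The count of 54 and the 42-dose rule come from protocol 10.1.3 and SAP 7.2. The 75% and 125% limits come from protocol 9.4.6, 9.6.11 and 9.6.12. Visit 3 is at Day 29 ± 2. Let d be the date of discontinuation minus the date of first application, in days.

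**The plan's own figures.** 28 × 2 = 56, which reproduces the completer denominator. 54 = 56 − 2, which requires two pre-test doses to be removed; the documents do not show how the 12-hour hold removes two. 0.75 × 56 = 42, so the 42-dose rule is 75% of 56.

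**Early discontinuers.** As printed: listed % = applications / min(56, d). On doses due, with 56 planned: applications / min(56, 2d).

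| d | Applications | Doses due | As printed | On doses due |
|---|---|---|---|---|
| 14 | 28 | 28 | 28/14 = 200% | 100% |
| 14 | 21 | 28 | 21/14 = 150% | 75% |
| 14 | 14 | 28 | 14/14 = 100% | 50% |
| 28 | 56 | 56 | 56/28 = 200% | 100% |
| 30 | 56 | 56 | 56/30 = 186.7% | 100% |

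For d from 1 to 28 the ratio of the two percentages is 2d/d = 2. It falls after that because no more doses come due. With 54 planned, the ratio is exactly 2 up to d = 27 (2 × 27 = 54) and 54/28 = 1.93 at d = 28. For d up to 28 on 56, a listed 75% to 125% corresponds to 0.75d/2d = 37.5% to 1.25d/2d = 62.5% of doses due.

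**The cap.** The latest in-window Visit 3 is Day 31, so d is at most 30 and a cap of 56 on a day count never takes effect. Applied to 2d, the cap takes effect at d = 28, the planned treatment length. This points to a multiplier omitted in drafting.

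**Day counting.** With 2d at d = 14 (28 doses due), one or two doses on the discontinuation day give 29/28 = 103.6% or 30/28 = 107.1%. Counting both end days gives 2(d + 1) = 30, and 30/30 = 100%. At d = 0 both the printed rule and a bare 2d have a zero denominator; 2(d + 1) gives 2.

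**56 against 54.** A completer who applies all 54 doses lists at 54/56 = 96.4%.

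**The two inclusion rules**, reading scheduled doses as the full course, as 9.4.6 describes it:

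- Floor on 56: 0.75 × 56 = 42, so the rules agree. 41 doses is 73.2% and fails both.
- Floor on 54: 0.75 × 54 = 40.5, so 41 doses (75.9%) passes the percentage rule and fails the 42-dose rule.
- Ceiling on 56: 1.25 × 56 = 70, so it is passed at 71 or more doses. Ceiling on 54: 67.5, so at 68 or more. Dosing twice a day through Day 30 is 60 doses, below both.

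**The case against.** The best defence is that little depends on this. The formula is a note inside a shell, and SAP section 8 says the shells may not reflect every aspect of the study and that footnotes will be modified as needed. The intent is easy to infer from the completer branch just above it, and the doubled brackets suggest that a term dropped out, perhaps only in the PDF text. L16.2.5.1 also prints total doses and the first and last dose dates, so a 200% entry would stand out. SAP section 7 plans no analysis of compliance.

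All of that stands as an argument about weight. It does not make the printed rule right: a programmer who follows it literally produces wrong percentages, and a half-adherent patient shown at 100% would not stand out.

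A reader might infer that the doubling changes who enters the primary HPA analysis. The documents do not support this, because inclusion and the exclusion listing both use an absolute count of 42 doses. A reader might also infer that it corrupts the study-drug non-compliance row in T16.1.9.2 or inclusion under protocol 9.4.6. That would follow only if the listed percentage were used there. No section says so, and protocol 9.6.11 and 9.6.12 verify compliance from the diaries.

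On 56 against 54, the defence notes fairly that the lower figure carries its own explanation, and that SAP 7.2 repeats protocol 10.1.3 unchanged, so SAP 7.7 had no change to record there. The listing still uses a different denominator from the section that defines the analysis.

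**Conclusion.** The early-discontinuer denominator is wrong as written. It doubles the listed compliance for any d from 1 to 28 on a planned count of 56, and by slightly less after that. The effect is limited to one column of one listing, and the HPA suppression proportion under SAP 7.2 does not change. This rests on the extracted text being complete, on d being a plain date difference, and on the percentage not feeding any other output.

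The other two differences are real but secondary. The planned count moves a fully dosed completer between 96.4% and 100%. The inclusion rules part only at exactly 41 doses on a base of 54, or at 68 or more doses (71 or more on 56). That comparison takes scheduled doses as the full course. If the sponsor means doses due up to discontinuation, the rules would part further (28 of 28 doses at d = 14 is 100% but below 42), which is another reason to state the rule once. Severity: minor.

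**What to change.** 1. Check the source PDF for a dropped multiplier. If there is none, change the early-discontinuer denominator in L16.2.5.1 to min(P, 2 × (date of discontinuation − date of first application)). This keeps the SAP's own dates.
2. State one convention for counting the first and last day, apply it to numerator and denominator alike, and make sure it gives a non-zero denominator at d = 0.
3. Settle one planned count P, and reconcile L16.2.5.1 (56) with SAP 7.2 and protocol 10.1.3 (54).
4. State in the SAP which inclusion rule governs the HPA analysis, reconciling protocol 9.4.6 with protocol 10.1.3 and SAP 7.2.
5. Say whether the listed percentage feeds T16.1.9.2.

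All of this should be done before database lock. The choice of count and rule is the sponsor's.

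Cost: a SAP clarification is enough for the formula. The date of discontinuation is not a column of L16.2.5.1, so its source should be named or the column added. Any change to protocol text would need an amendment with IRB approval under protocol 11.2.3.
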